5.2 Recruitment Methods

Recruitment

Data from VA medical records will be obtained via the Clinical Data Warehouse (CDW) to identify patients with prediabetes. Patients seen at VAAHS in the past year (January 2019 - December 2019) with a A1c recorded over that time period will be screened.

Eligible patients will be sent a letter inviting them to participate in the study. We estimate that 10% of eligible individuals will enroll in our study. Thus, we will send study invitation letters by postal mail to up to 220 potentially eligible individuals. The letter will explain the purpose of the study. A phone number will be provided to individuals to allow for them to opt-in to study participation or opt-out of future contact by the study team. A member of the study team will contact individuals who opt-in. The study team member will confirm individuals' study eligibility and answer any questions. If up to 30 veterans are not recruited via the opt in approach, a member of the study team member will call those individuals that did not opt-out and invite them to participate.

All interested and eligible individuals will be invited to an in-person recruitment session. The purpose of this session will be to explain the program and dietary approach (i.e., low-carbohydrate, high-fat) in detail. This session is necessary to ensure full and proper informed consent. In our prior pilot work at Canton Health Center, program participants informed us during qualitative interviews that they wished for additional education about the dietary approach to alleviate concerns regarding dietary fat and cholesterol intake. Because this is

information that participants should, ideally, understand prior to enrollment, we will deliver a brief presentation (~20-30 minutes) during this recruitment session. An additional 20-30 minutes will be allocated to answering individuals' questions. Afterwards, those interested in study participation will be asked to provide written, informed consent and to complete a baseline survey and laboratory testing.

Participants will receive a Visa or Amazon gift card to compensate you for completing each of the following study activities:

- Baseline labs (\$25)
- 6-month survey (\$25)
- 6-month labs (\$25)
- 6-month interview (\$25)
- 12-month survey (\$25)
- 12-month labs (\$25)
- 12-month interview (\$25)

5.3 Informed Consent Procedures

Informed consent will be obtained prior to study enrollment. This will be obtained in person by study staff. Participants will have the opportunity to ask any questions prior to signing the consent. We expect that there will be no special considerations required for obtaining consent.

5.4 Inclusion/Exclusion Criteria

We will recruit individuals based on the following inclusion criteria: (1) age \geq 18 years; (2) prediabetes (defined as A1c 5.7% to 6.4% drawn within 12 months of study start date); (3) body mass index \geq 25 kg/m²; (4) serum lipid levels drawn within 12 months of study start date; (4) willingness to participate in group-based classes, and able to engage in at least light physical activity such as walking. The participants must have established primary care at the AAVA (defined as at least one office visit within 12 months of the study start date). This will ensure that participants can have access to a medical provider for medication changes and side effective management, if necessary.

We will exclude individuals based on the following criteria: (1) history of type 1 diabetes or type 2 diabetes; (2) current participation in another lifestyle or behavior change program or research study; (3) vegetarian or vegan lifestyle; (4) history of bariatric surgery; (5) inability to read, write, or speak English; (6) inability to provide informed consent; or (7) women who are pregnant or intend to become pregnant during the intervention period.

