7.0 Special Human Subject Categories

8.0 Recruitment

8.1 Describe the inclusion criteria for this protocol, along with the rationale for these criteria. This includes retrospective chart reviews. *Use bullet or numbering format.

We will recruit Veterans from AAVA primary care clinics.

Inclusion criteria:

- Age \geq 18 years
- Prediabetes (defined as A1c 5.7% to 6.4% drawn within 12 months of study start date)
- Lipids drawn within 12 months of study start date
- Body mass index \geq 25 kg/m²
- Willingness to participate in group-based classes
- Able to engage in at least light physical activity such as walking
- Established primary care at the AAVA (defined as at least one office visit within 12 months of the study start date). This will ensure that participants can have access to a medical provider for medication changes and side effective management, if necessary.

We plan to interview LC-DPP coaches and Primary care providers (PCPs) in the future. However, this component of the study is not yet fully developed. An amendment will be submitted and we will obtain approval for all recruitment activities and materials prior to commencement of these interviews.

8.2 Describe the exclusion criteria for this protocol (including retrospective chart reviews). Include the rationale for excluding any patients who might particularly benefit from participation. Also address whether subjects enrolled in another protocol are excluded. *Use bullet or numbering format.

Exclusion criteria are:

- History of type 1 diabetes or type 2 diabetes
- Current participation in another lifestyle or behavior change program or research study
- Vegetarian or vegan lifestyle
- History of bariatric surgery
- Inability to read, write, or speak English
- Inability to provide informed consent
- Women who are pregnant or intend to become pregnant during the intervention period
- Individuals with LDL > 190
- Individuals with a history of eating disorders
- Individuals with advanced kidney disease (defined as eGFR < 45 mL/min)

8.3 Will there be more than one group/type of subject recruited for the protocol?

Yes No

8.4

Describe the recruitment strategy for the just, fair, and equitable recruitment and selection of subjects, and reference recruitment procedures as cited in the scientific narrative to include the following: Plans for recruitment of all subjects (or selection of subjects as in record review). This description must include:

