As noted above in the description of inclusion and exclusion criteria, these data will be used to determine if patients meet the following criteria: BMI \geq 25 and HbA1c 5.7%-6.4% in the prior 12 months.

10.46 Specify the date range(s) of all PII/PHI to be collected.

April 2019 - April 2020

10.47 The use or disclosure of PHI involves no more than a minimal risk to the privacy of individuals.

Agree

Explain why risk is no more than minimal

We have extensive experience maintaining the confidentiality of PHI for research purposes. A cross-

walked file will be maintained to link participants to unique, de-identified study IDs. The crosswalk file will be kept in a separate, secure folder. Access to this folder will be restricted to study team members. All data will be maintained in restricted folders on the VA network.

10.48 A plan exists to move all identifiable data to a location accessible only to the Research Service Records Liaison or an honest broker at the earliest opportunity consistent with conduct of the research, unless there is a health or research justification for retaining the identifiers or such retention is otherwise required by law. These records will be disposed of when they have met their Records Control Schedule or other contractual obligation, whichever is longest.

Agree

Describe the plan:

All research data will be de-identified at the termination of the study, if not sooner. Study data will be moved to the CCMR data archive and destroyed by the CCMR data manager six (6) years following the end of the Fiscal Year after completion of the research project as described in the Records Control Schedule.

10.49 The plan to protect the identifiers from improper use and disclosure is adequate.

Agree

Describe the plan:

Protection of screening data: A cross-walk file will be established that includes patient names linked to study ID numbers assigned by the CDW. Unique study ID numbers are needed to link multiple records for a patient in CDW. The cross-walk file will be kept in a folder on the VA network that is restricted to access by members of the study team. The study ID number will be maintained with the health data pulled from CDW in a separate, access restricted folder on the VA network.

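### The IRB form excludes ten groups, but both eligibility lists in the scientific narrative stop at seven and omit LDL >190, eating-disorder history and eGFR <45 mL/min

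*Protocol*

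**What the plan says.** Eligibility is set out in three places: IRB form sections 8.1 and 8.2 (the file holds two copies of the form, and they agree), the Study Population part of narrative section 5.1, and narrative section 5.4.

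Form 8.2 lists ten exclusions. The last three are "Individuals with LDL > 190", "Individuals with a history of eating disorders" and "Individuals with advanced kidney disease (defined as eGFR < 45 mL/min" (closing bracket cut from the quote).

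Narrative 5.1 and 5.4 each number their exclusions from (1) to (7) and end identically: "6) inability to provide informed consent; or (7) women who are pregnant or intend to become pregnant during the intervention period". The *or* before item (7) marks the list as complete.

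On inclusion, form 8.1 requires "Lipids drawn within 12 months of study start date" and narrative 5.4 requires "4) serum lipid levels drawn within 12 months of study start date". Narrative 5.1 has no such item.

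**The concern.** The same person can be excluded by the form and eligible under the narrative. The narrative cannot be set aside as background. Its section 5.4 is the one headed for eligibility, and the form relies on the narrative elsewhere: form 8.4 asks for recruitment procedures to be referenced as the narrative gives them, and form 9.9 sends the reader to the narrative for the safety monitoring plan. Neither text is marked as superseded.

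What is at stake is who receives the diet. Narrative 5.1 sets carbohydrate at 20-35 g a day, aims for nutritional ketosis, and suggests roughly 80-120 g of protein a day. The documents give no reason for the three extra exclusions. For LDL the link is nonetheless plain, because narrative section 6.0 says LDL can rise on a low-carbohydrate diet.

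**Working it through.** There is no planned figure to reproduce. The check compares the lists item by item.

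| Item | Form 8.1/8.2 (both copies) | Narrative 5.1 | Narrative 5.4 |
|---|---|---|---|
| Seven exclusions, from diabetes history to pregnancy | listed | listed | listed |
| LDL >190 | excluded | absent | absent |
| History of eating disorders | excluded | absent | absent |
| eGFR <45 mL/min | excluded | absent | absent |
| **Number of exclusions** | **10** | **7** | **7** |
| 12-month lipid result (inclusion) | required | absent | required |

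- Exclusions missing from each narrative list: 10 − 7 = 3, the same three in both; 3/10 = 30% of the form's items. This counts list entries and does not measure effect.
- Lipid inclusion criterion: missing from 1 of 3 lists (narrative 5.1).
- In narrative 5.4 the lipid item is numbered (4), and so is the item after it. This is consistent with an edit that was not carried through, though the documents do not say so.

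Next, would a person admitted under the narrative list be picked up later? Form 6.26 limits the study blood tests to A1c and lipids. Narrative 5.5 has the baseline sample taken after consent.

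- **LDL >190:** probably seen at baseline. Form 9.7 and narrative 5.7 allow withdrawal of someone who becomes ineligible, but whether this person is ineligible depends on which list is used.
- **eGFR <45 mL/min:** not detected, because no study test measures kidney function.
- **Eating-disorder history:** not detectable by a blood test.

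The gap is therefore partly covered for LDL. For the other two, the study blood tests offer no cover.

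**The case against.** **The lists can be combined.** They do not contradict each other logically, and applying both gives ten exclusions. That is right, and it is why the claim is that people *could* be enrolled wrongly. A reader might infer that they *would* be, but that assumes staff use the narrative alone, which the documents do not show. Equally, no text tells staff to combine the lists or to follow the stricter one.

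**LDL is monitored.** Narrative 6.0 has lipids checked at 0, 6 and 12 months, with results sent to primary care and possible changes to medication or diet. This stands and weakens the LDL part of the concern. It does nothing for kidney function or eating disorders.

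**Screening may already cover all three.** A reader might infer that the chart screen checks only BMI and A1c, since form 10.45 says "these data will be used to determine if patients meet the following criteria" and then names just those two. The documents do not support that reading:

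- The same sentence opens by pointing back to the inclusion and exclusion criteria, and it names none of the ten exclusions, not even diabetes history. It is a partial summary.
- The phrase "with a A1c recorded over that time period will be screened" in narrative 5.2 defines the pool to be screened, not the criteria applied to it.
- Form 13.10 says charts are used to identify eligible patients, form 13.14 lists laboratory results among the screening data, and form 10.44 adds problem-list diagnoses.
- Eligibility is also confirmed by telephone before consent (form 8.4, narrative 5.2). The script is an attachment that is not in the file and may cover some of these items.

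No claim is made here that the screen would miss the three groups. What remains is that a general reference to eligibility criteria cannot settle which list is meant.

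**Conclusion.** The point holds as an inconsistency between the form and the scientific narrative. Three of the form's ten exclusions are absent from both narrative lists, one inclusion criterion is absent from narrative 5.1, and no rule of precedence is given. Staff who work from the narrative could enrol people the form excludes. The exposure is greater for low eGFR and eating-disorder history than for high LDL, which the baseline sample would probably show.

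This rests on two assumptions: that staff may work from either text, and that the unseen telephone script does not resolve the difference.

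A reader might want a number of participants affected. The documents give no prevalence for any of the three conditions, so none can be derived. A reader might also infer that the feasibility results are affected. Narrative 5.5 defines uptake as recruits divided by people invited, whichever exclusion list is used, and no stated statistical figure changes. The point concerns eligibility and safety, and should be corrected in the text.

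**What to change.** 1. Put the same ten exclusions in narrative 5.1, narrative 5.4 and form 8.2.
2. Add the 12-month lipid inclusion criterion to narrative 5.1, and correct the repeated number (4) in narrative 5.4 in the same edit.
3. State that the LDL, eGFR and eating-disorder exclusions are applied at the existing chart and telephone eligibility check before consent, using whatever chart values are available.

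Do not add a requirement for a recent eGFR. No current list has one. It would be a new entry rule, and it would raise the question of whether people without a value are tested, excluded or enrolled.

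The cost is wording in the narrative, with no new test, visit or analysis. The downside is that a few people eligible under the narrative list would be screened out.

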5.5 Study Evaluations

Quantitative Data source

a) Weight

Participants will be encouraged to self-monitor weight using a home scale although this

data will not be collected by the study team. In accordance with standard DPP operating procedure, participants will be weighed in a private room prior to each session and their weight will be recorded by a member of the study team.

b) Physical activity

In accordance with standard DPP operating procedure, participants will be encouraged to self-monitor physical activity minutes and to report this information to the lifestyle coach at the start of each session.

c) Laboratory metrics

We will evaluate change in A1c and lipids over the study period. Baseline laboratory studies will be obtained once individuals have consented to participate in this study. Repeat A1c and lipid levels will be drawn at 6 and 12 months.

d) Session attendance

Participants will be encouraged to attend all sessions and attendance will be recorded by the lifestyle coach.

e) Survey Data

At baseline, 6 months, and 12 months, study participants will be invited to complete a written survey. Paper copies will be given to individuals at session 15/16. Because we aim to obtain complete follow-up data, we will make efforts to collect survey responses from participants that are not present for session 15/16. We will send surveys to non-attendeess via postal mail. All individuals will be asked to return their survey to the study team via pre-paid envelope or in-person delivery. The survey will assess domains related to the following: global health and well-being; sleep; food cravings; stress eating; hunger; energy; mood; physical symptoms, neuropathic symptoms (e.g., tingling, burning in feet); side effects; and cost of food. At baseline, we will ask participants to provide sociodemographic characteristics. At 6 months and 12 months, participants will be asked to provide feedback about the study and will receive compensation for each survey.

Qualitative Data Sources

Participants will be encouraged to maintain a log of food intake and physical activity. Each week, the lifestyle coach will review the logs and provide individual feedback. We will retain copies of participants' logs from their first 2 weeks in the study and their last 2 weeks in the study. In this way, we can qualitatively assess changes in dietary habits and physical activity.

We will conduct qualitative, semi-structured interviews with a purposive sample of LC-DPP participants to solicit participant feedback on the LC-DPP curriculum and to better understand barriers to (e.g. food cravings, side effects) and facilitators of (e.g. satiety, energy) intervention adherence. The participants interviewed (n=14) will be purposively sampled based on weight loss outcomes (e.g., achievement vs. non-achievement of at least 5% body weight loss). Participants' experiences with the program and barriers to and facilitators of adherence to the diet will be explored. Participants will receive Visa and/or Amazon gift cards to compensate them for their time after completing the 6 and 12-month interview.

We will conduct interviews with VA LC-DPP coaches and VA primary care providers to evaluate perceptions about the diet and the program. We will explore coaches' experiences with leading the program and solicit feedback on challenges and opportunities for improvement.

Outcomes

Primary Measures: Feasibility and Acceptability

Primary outcome measures are feasibility (e.g., uptake and retention rates) and acceptability (e.g., session attendance, qualitative feedback). LC-DPP uptake rate will be defined as the number of participants recruited to the intervention divided by the total number of individuals invited to participate. LC-DPP retention rate will be determined by calculating the rate of completion of the 6-month and 12-month surveys. Because some individuals may remain engaged in the intervention (e.g., communicated via phone or email with the coach) despite personal barriers to in-person session attendance, we will use survey completion rate rather than a session attendance threshold (e.g., attendance at 9 core sessions) to measure study retention.

Intervention acceptability will be determined by calculating the rate of attendance at core and maintenance sessions. To further understand the program's acceptability, we will conduct semi-structured interviews at 6 and 12 months. During interviews, we will explore participants' general experiences with the intervention as well as specific facilitators of and barriers to VLCD adherence.

Secondary Measures:

Change in body weight: Body weight will be measured and recorded at each attended session. We will calculate average body weight change and percent body weight loss at the end of the program's core phase (6 months) and maintenance phase (12 months). Among session non-attendees, we will attempt to schedule 6- and 12-month weigh-ins at participants' convenience within 2 weeks of the final core and maintenance sessions. All weights will be obtained using the same calibrated scale.

Change in HbA1c: We will calculate change in HbA1c from baseline to 6 and 12 months

Change in lipids: We will calculate change in triglycerides and total cholesterol/HDL ratio from baseline to 6 months and 12 months.

Change in survey measures: We will calculate change in self-reported survey measures from baseline to 6 months and 12 months.

Fidelity: We will measure intervention fidelity (i.e., extent to which components of an intervention are delivered as intended) using quantitative measures adapted from the literature²⁶ as well as qualitative interview feedback from participants and dietitians.

